2.2 SAMPLE SIZE DETERMINATION

The sample size was estimated on the basis of data from Study WA25046 (ORATORIO).

A two-group test of equal exponential survival is used to determine the sample size for the composite 12-week CDP of EDSS and 9-HPT. With a sample size of 1000 patients (of which at least 350 patients are expected in the MRI-active population), a double-blind treatment phase of 144 weeks, an annual dropout rate of 10%, and a randomization ratio of 1:1, it is expected that approximately 340 events will be observed in all randomized patients (placebo progression rate: 40%), which will provide approximately 80% power to detect a hazard ratio (HR) of 0.70 at a type I error rate of 0.0146 and approximately 75.5% power to detect a HR of 0.75 at a type I error rate of 0.05. Likewise, it is expected that approximately 122 events will be observed in the MRI-active subgroup (placebo progression rate: 44%), which will provide approximately 78% power to detect a HR of 0.60 at a type I error rate of 0.04.

Operating characteristics (power and expected total number of events) for true underlying HR values of 0.60, 0.70, and 0.75 are provided in [Table 4](#) for all randomized patients and the MRI-active subgroup.

Table 4 Operating Characteristics for Possible True Underlying Hazard Ratio Values

	MRI-Active Subgroup	All Patients Randomized	All Patients Randomized
Expected number of events	122	340	340
Expected proportion of placebo patients with composite events at Week 120	44%	40%	40%
2-sided alpha for the log-rank test	0.04	0.0146	0.05
Power	78%	80%	75.5%
Detectable hazard ratio	0.60	0.70	0.75

MRI = magnetic resonance imaging.

Note: Operating characteristics are based on the following assumptions: event times are exponentially distributed, and patients are followed for 144 weeks.

It should be noted that the type I error rate to be used for the testing in all randomized patients will be adjusted depending on the proportion of events in the MRI-active subgroup at the primary analysis.

3. **ANALYSIS SETS**

The analysis sets are defined in [Table 5](#).

Table 5 Participant Analysis Sets

Participant Analysis Set	Description
Full analysis set	All randomized participants; participants will be included in the analyses according to the treatment to which they were assigned.
MRI activity analysis set	All randomized participants with MRI activity, defined as presence of T1 Gd+ lesion[s] and/or new and/or enlarging T2 lesion[s] as detected by MRI scans during the screening phase; participants will be included in the analysis according to the treatment to which they were assigned.
Immunogenicity analysis set	All randomized participants with at least one ADA assessment; participants will be grouped according to treatment received at first exposure or, if no treatment is received prior to study discontinuation, according to treatment assigned.

Participant Analysis Set	Description
Pharmacokinetic analysis set	All randomized participants who have measurable concentrations of ocrelizumab unless major protocol deviations or unavailability of information (e.g., exact blood sampling time) occurred or if data are unavailable, not plausible, or incomplete which may interfere with PK evaluation. Excluded cases will be documented together with the reason for exclusion; participants will be grouped together.
Safety analysis set	All participants who received at least one infusion (partial or complete) of study drug; participants will be included in the analyses according to the treatment that they actually received.
Ocrelizumab exposed analysis set	All randomized participants who received at least one infusion (partial or complete) of ocrelizumab (study drug, PDP OCR, OLE OCR or commercial ocrelizumab); participants will be grouped together.
No major protocol deviation (MRI activity) analysis set	All participants included in the first supplementary analysis as described in Section 4.2.4; participants will be included in the analysis according to the treatment to which they were assigned.
No major protocol deviation analysis set	All participants included in the first supplementary analysis of Section 4.2.7 participants will be included in the analysis according to the treatment to which they were assigned.

ADA = anti-drug antibody; MRI = magnetic resonance imaging; OCR = ocrelizumab; OLE = open-label extension; PDP = post-double-progression; PK = pharmacokinetic.

MRI activity analysis set will be used in the analysis of the co-primary estimand 1.

Full analysis set (FAS) will be used in the analysis of the co-primary estimand 2 and secondary estimands. For exploratory efficacy endpoints, FAS and MRI activity analysis sets will be used. Safety analysis set (SAS) and ocrelizumab exposed analysis set will be used to summarize safety data. No major protocol deviation (MRI activity) analysis set will be used in the first supplementary analysis as described in Section 4.2.4. No major protocol deviation analysis set will be used in a supplementary analysis described in Section 4.2.7 .

4. STATISTICAL ANALYSES

4.1 GENERAL CONSIDERATIONS

As per the EMA guideline on multiplicity issues in clinical trials (EMA, 2017) and the FDA guidance for industry on multiple endpoints in clinical trials (FDA, 2022) multiple primary endpoints are designated as co-primary endpoints if study success is defined by a positive outcome in all primary endpoints.

In this SAP, the terminology co-primary endpoint and co-primary estimand is used although study success is defined by a positive outcome in at least one of the two co-primary endpoints, analogous to multiple primary endpoints.

For all continuous variables for which descriptive statistics are reported, the following will be reported: the number of observations, the mean, median, standard deviation, and minimum and maximum. The 25th and 75th percentiles (Q1 and Q3) will also be reported for selected tables. Descriptive summaries of discrete data will include frequencies expressed in terms of number and percentage of patients.

All primary and secondary efficacy endpoints will be stratified by/adjusted for:

- MRI activity, defined as any T1 Gd+ lesion(s) and/or new and/or enlarging T2 lesion(s) during the screening period (yes vs. no)
- Age (≤ 55 . vs. > 55)
- EDSS score (≤ 6.5 vs. > 6.5)
- Region (two regions: European Union, United Kingdom, and Canada vs. other)

The baseline is defined as the most recent value prior to first dose administration (or up to and including the date of randomization for non-treated patients), unless specified otherwise.

The baseline MRI is defined as the most recent MRI prior to randomization.

For EDSS and 9-HPT, baseline is defined as the most recent value prior to randomization.

There will be no imputation of the baseline outcome value, with the consequence that participants missing the baseline outcome measure will not contribute to the analyses which use change from baseline of a given outcome measure as the dependent variable.

For analysis purposes, the time of treatment discontinuation will be defined as 24 weeks after the last dose prior to the date of treatment discontinuation recorded in the electronic Case Report Form (eCRF).

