4.5.10 Mandatory and Optional MRI Sequences

MRI will be used to monitor CNS lesions in patients with MS and potentially other pathophysiology, such as inflammation and neurodegeneration. Mandatory MRI scans (formally known as 'brain MRI') will be obtained in all patients at study visits as indicated in [Appendix 1](#), [Appendix 2](#), [Appendix 3](#), and [Appendix 4](#).

During the screening phase, two mandatory MRI scans (performed at least 6 weeks apart, but not more than 24 weeks apart) or one MRI with the mandatory sequences that can be compared with a historical MRI acquired in the previous 1 year will be performed to assess the patient's MRI activity level. MRI activity is defined as the presence of any T1 Gd+ lesion(s) and/or new and/or enlarging T2 lesion(s) during the screening period (see also Section 3.1). If the presence of new or enlarging lesions is ascertained, the patient will be stratified to the MRI-active subgroup. The MRI performed closer to randomization (i.e., either the second MRI scan at screening or the [only] screening MRI scan in the case where a historical scan was used for the assessment of MRI activity) will be considered as baseline MRI for the study analyses and will be captured under the baseline visit in the eCRF. Note that this baseline scan should be obtained maximum 6 weeks before but at least 10 days prior to performing the baseline visit to allow time for the centralized reading center to assess its quality and for potential re-scans if needed.

Postbaseline, the mandatory MRI scans will be obtained in all patients at Weeks 24, 48, and 72. From Week 72 onward, MRI scans will be performed every 48 weeks (i.e., at Week 120, 168, etc.). In addition, mandatory MRI scans will be obtained in patients who withdraw from study treatment (at withdrawal visit) if one was not performed during the prior 4 weeks. Mandatory MRI scans should occur within a window of ± 4 weeks of the scheduled visit, as per the schedules of activities (see [Appendix 1](#), [Appendix 2](#), [Appendix 3](#), and [Appendix 4](#)). At the Week 120 visit for patients switching to PDP OCR treatment, mandatory MRI scans should be obtained within 4 weeks before the Week 120 visit.

The mandatory MRI sequences are comprised of both brain and axial cervical spinal sequences if site technology is available, and data from these scans will contribute measurements for the key MRI secondary endpoints as well as novel exploratory

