4.3.1 Estimands for Time to Event Endpoints

All secondary estimands which focus on the analysis of time to event endpoints have the same estimand attributes (except for Endpoint attribute) and estimation method as for the co-primary estimand 2 (Section [4.2.5](#)).

The time to 12-week CDP in 9-HPT and time to 12-week CDP in EDSS are the individual components of the composite 12-week CDP as defined in Section [4.2.1](#).

The time to 24-week CDP in 9-HPT and time to 24-week CDP in EDSS will be defined over a 24-week confirmation window (≥ 161 days) for the disability progression.

4.3.2 Estimand for Annual Rate of Change from baseline in radius of total volume of T2 lesions

Estimand: The estimand is the mean difference in annual rate of change from baseline in radius of total volume of T2 lesions between the experimental and control arms in patients with PPMS, including patients later in their disease course, where no treatment discontinuation nor initiation of another MS DMT or commercial ocrelizumab can occur.

Estimator: A random coefficient regression model (RCRM) will be used to quantify the mean difference in annual rate of change from baseline in radius of total volume of T2 lesions between the experimental and control arms. The mean structure of the model is as follows:

$$E[Y_{ij} | time_{ij}, T_i, X_i] = time_{ij}(\beta_0 + \alpha X_i + \beta_1 T_i + u_i),$$

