where Y_{ij} represents change in the cube root of total volume of T2 lesions from baseline at visit j for patient i , $time_{ij}$ is the time from baseline in years at visit j for patient i , T_i is an indicator such that $T_i = 1$ if patient i was randomized to the ocrelizumab arm and $T_i = 0$ otherwise, X_i is a vector containing the cube root of the baseline total volume of T2 lesions and randomization stratification factors for patient i , α is a vector of regression coefficients for X_i , β_0 is the adjusted mean of the annualized rate of change in radius of total volume of T2 lesions for the placebo arm, β_1 is the adjusted mean difference in the annualized rate of change in radius of total volume of T2 lesions between the experimental and control arms, and u_i is a subject-specific random effect that follows a mean zero normal distribution with unknown common variance for all patients. Only scheduled visits will be included in the analysis. The statistical significance of the estimated mean difference will be calculated by using the Wald test, where the standard error is estimated using the robust sandwich variance estimator.

In order to estimate the aforementioned estimand, the following intercurrent event handling strategies will be applied:

Withdrawal from treatment and no initiation of another MS DMT or commercial ocrelizumab: All data after treatment discontinuation will be treated as missing following the hypothetical strategy.

Withdrawal from treatment and initiation of another MS DMT or commercial ocrelizumab: All data after treatment discontinuation will be treated as missing following the hypothetical strategy.

Sample Statistical Analysis System code can be found below (Statistical Analysis System code is regarded as “draft” until fully validated at the analysis stage):

```
PROC MIXED DATA=dataset empirical;  
CLASS USUBJID ARMCD StratificationFactors;  
MODEL AVAL_N= ARMCD Baseline StratificationFactors / solution cl;  
RANDOM intercept / subject=USUBJID type=un;  
run;
```

where AVAL_N is the change from baseline in the cube root of the total volume of T2 lesions divided by time at each scheduled visit, and Baseline is the cube root of the total volume of T2 lesions at baseline.

4.3.3 Estimand for Annual Rate of Percent Change from Week 24 in Total Brain Volume

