4.4.5 Estimands for Rate of Change of Continuous MRI Endpoints

Estimand: The estimand is the mean difference in the endpoint between the experimental and control arms in patients with PPMS, including patients later in their disease course, where no treatment discontinuation nor initiation of another MS DMT or commercial ocrelizumab can occur.

Endpoints:

- Annual rate of percent change from baseline and from Week 24 in cervical spinal cord volume on MRI scans
- Annual rate of change from baseline in radius of total non-enhancing T1 lesion volume on MRI scan of the brain

The same population definition, intercurrent events handling strategies and estimator will apply as for the annual rate of change from baseline in radius of total volume of T2 lesions (Section 4.3.2).

The estimand for rate of change of continuous MRI endpoints in the MRI-active subgroup will be similar except the population will be patients with PPMS, including patients later in their disease course, as defined by the study inclusion and exclusion criteria (see Sections 4.1.1 and 4.1.2 of the protocol), with MRI activity (see Section 2.1.1 of the protocol).

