4.4.6 Estimands for Expected Counts at each Scheduled Visit

Estimand: The estimand is the ratio of the mean endpoint between the experimental and control arms in patients with PPMS, including patients later in their disease course, where no treatment discontinuation nor initiation of another MS DMT or commercial ocrelizumab can occur.

Endpoints:

- The number of Gd-enhancing T1 lesions as detected by mandatory MRI, overall and at each scheduled visit
- The number of new or enlarging T2 hyperintense lesions as detected by mandatory MRI, overall and at each scheduled visit

Summary Measure and Primary Estimator: Separate negative binomial models will be fitted to the data on the endpoints at each scheduled visit and overall for the total count. The mean function of the model will be parameterized using the log link function and the linear predictor will include as an offset either the log number of MRI scans for Gd-enhancing T1 lesions or log time in years of scan relative to baseline for new or enlarging T2 hyperintense lesions, an indicator variable for the assigned treatment and the randomization stratification factors as independent variables. The statistical significance of the estimated ratio of means will be calculated by using the Wald test.

In order to estimate the aforementioned estimand, the same intercurrent event handling strategies as those for brain volume in Section 4.3.2 Section 4.3.3 will be applied.

The estimand for expected counts at each scheduled visit in the MRI-active subgroup will be similar except the population will be patients with PPMS, including patients later in their disease course, as defined by the study inclusion and exclusion criteria (See Sections 4.1.1 and 4.1.2 of the protocol), with MRI activity (see Section 2.1.1 of the protocol).

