4.5.1.2 Treatment Duration and Duration under Observation Definitions

Treatment duration during the DBT and FU1 phases will be calculated as follows:

(Date of the last recorded treatment observation during the DBT and FU1 phases* – Date of first dose of the DBT phase) + 1

*The date of the last recorded treatment observation during the DBT and FU1 phases is defined as the earliest between:

- date of last dose received during the DBT phase + 24 weeks
- last day prior to entering in FU2 as per the subject disposition eCRF page
- last day prior to the first OLE dose
- last day prior to the first PDP OCR dose
- last day prior to start of commercial ocrelizumab treatment or other MS DMT
- clinical cutoff date (CCOD) for the primary analysis reporting
- date of discontinuation from the study as indicated on the subject disposition eCRF page
- date of death

Treatment duration for all ocrelizumab exposed patients will be calculated as follows:

(Date of the last recorded treatment observation for all ocrelizumab exposed patients*–Date of the first dose of ocrelizumab (study drug, PDP OCR, OLE OCR or commercial ocrelizumab))+ 1

*The date of the last recorded treatment observation for all ocrelizumab exposed patients is defined as the earliest between:

- date of last dose of ocrelizumab (study drug, PDP OCR, OLE OCR or commercial ocrelizumab)+24 weeks
- last day prior to start of other MS DMT (not including commercial ocrelizumab)
- date of discontinuation from the study as indicated on the subject disposition eCRF page
- CCOD for the primary analysis reporting
- date of death

The duration under observation during the DBT and FU1 phases for a patient will be calculated as follows:

(Date of last observation during the DBT and FU1 phases*–Date of first infusion in the first dose)+ 1

*Date of last observation during the DBT and FU1 phases is defined as the earliest between:

- the latest recorded date in all CRF and non CRF data prior to CCOD
- last day prior to entering in FU2 as per the subject disposition eCRF page
- last day prior to the first OLE dose
- last day prior to the first PDP OCR dose
- last day prior to start of commercial ocrelizumab treatment or other MS DMT
- date of discontinuation from the study as indicated on the subject disposition eCRF page
- date of death

The duration under observation for all ocrelizumab exposed patients will be calculated as follows:

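### The MRI analyses remove switchers' data only from last dose + 24 weeks, so a scan taken after an earlier start of another MS drug is kept, contrary to the stated estimand

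*SAP*

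**What the plan says.** **The estimand.** SAP 4.3.2 (T2 lesion radius) and 4.3.3 (brain volume) each target the difference between arms in a setting "where no treatment discontinuation nor initiation of another MS DMT or commercial ocrelizumab can occur".

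**The data rule.** Both sections list two intercurrent events: stopping treatment without another MS drug, and stopping treatment and then starting another MS DMT or commercial ocrelizumab. The rule is the same for both: "All data after treatment discontinuation will be treated as missing following the hypothetical strategy". The start of the new drug is not itself a cut point.

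**The date.** SAP 4.1 fixes that date for analysis: "the time of treatment discontinuation will be defined as 24 weeks after the last dose", taking the last dose before the discontinuation date recorded in the eCRF. It has no limb for a switch that comes sooner.

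**Inheritance.** For the exploratory MRI rates (4.4.5), "The same population definition, intercurrent events handling strategies and estimator will apply" as for T2 lesions. For the lesion counts (4.4.6) the SAP applies "the same intercurrent event handling strategies as those for brain volume".

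**Elsewhere.** Safety treatment duration in SAP 4.5.1.2 is the earliest of several dates. They include last dose + 24 weeks and, separately, the "last day prior to start of commercial ocrelizumab treatment or other MS DMT". For the primary endpoint, SAP 4.2.2 either imputes an event at the start of the new treatment or works from assessments made before it.

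**The concern.** For a patient who simply stops, a 24-week allowance is understandable: Protocol Table 3 gives each dose a duration of 24 weeks. A switch is a different event. Once a new MS drug starts, a scan no longer represents the no-switch setting, even if it falls within 24 weeks of the last blinded dose. By giving both events the same rule, the SAP lets the switch have no effect on which scans are used.

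The 4.1 definition opens the gap. Other MS therapies are not permitted during the study treatment phase (Protocol 4.4.3), so a cut at the recorded discontinuation date would normally precede any switch. Moving the cut to last dose + 24 weeks can place it after the switch.

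At stake is the agreement between estimand and analysis for two secondary endpoints. They stand fifth and sixth in the hierarchy, which is tested at α = 0.05 only if both co-primary analyses succeed (SAP 2.1). The exploratory MRI rates and lesion counts are also affected.

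**Working it through.** The plan gives no figure on this point, so there is none to reproduce. The check sets the planned doses and scans against the cut.

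**Inputs**
- Doses at Weeks 0, 24, 48, 72, 96 and 120 (Protocol Table 3).
- Scans: "the mandatory MRI scans will be obtained in all patients at Weeks 24, 48, and 72", then every 48 weeks, so next at Week 120; window ±4 weeks (Protocol 4.5.10).
- FU1 scans: every 48 weeks (Protocol Appendix 2).
- Scans used in the slope models: "Only scheduled visits will be included in the analysis" (SAP 4.3.2; the same limit is in 4.3.3).
- Switching: allowed after discontinuation, with no minimum interval stated for other MS drugs (Protocol 4.4.3). Switchers stay under assessment in FU1 (Protocol 3.1.1.4).

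**Rule as written.** Cut = last dose + 24. A scan is kept if its date is on or before the cut. It is a scan on the new drug if the switch came before it.

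The protocol can be read in two ways on when a switcher is scanned, so both are shown (all entries are weeks). In the right-hand columns the next scan is counted as 48 weeks after the last scheduled scan.

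| Last dose | Cut | Scan after last dose and by the cut, double-blind calendar | Next scan, 48-weekly FU1 | By the cut? |
|---|---|---|---|---|
| 0 | 24 (26 from the second infusion) | 24 | 0 + 48 = 48 | no |
| 24 | 48 | 48 | 24 + 48 = 72 | no |
| 48 | 72 | 72 | 48 + 48 = 96 | no |
| 72 | 96 | none | 72 + 48 = 120 | no |
| 96 | 120 | 120 | 72 + 48 = 120 | yes |
| 120 | 144 | none | 120 + 48 = 168 | no |

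On the double-blind calendar at most one scheduled scan per switcher is affected, and none after a last dose at Week 72 or 120. On the 48-weekly reading only a last dose at Week 96 is exposed. If the 48 weeks run from FU1 entry, the next scan always falls after the cut.

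**Time on the new drug at a kept scan.** If the drug starts *s* weeks after the last dose and the scan is on the cut date, exposure is 24 − *s*. For illustrative starts:
- *s* = 4: 24 − 4 = 20 weeks
- *s* = 8: 24 − 8 = 16 weeks
- *s* = 12: 24 − 12 = 12 weeks
- *s* = 16: 24 − 16 = 8 weeks

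**Example.** Last dose Week 24, new drug at Week 32. The SAP cut is 24 + 24 = Week 48. A Week 48 scan, 48 − 32 = 16 weeks into the new drug, is kept. A cut at the earlier of Weeks 48 and 32 removes it. For this patient Week 48 is the only brain-volume slope observation (the reference is Week 24), one of two T2 observations (Weeks 24 and 48), and the whole contribution to the Week 48 lesion-count model.

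**One case that adds nothing to the slope.** If only dose 1 was given, a Week 24 scan on a new drug would be the brain-volume reference, with practically no later scan retained.

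**The case against.** The strongest reply is that the gap may catch few scans or none. FU1 patients are listed for MRI every 48 weeks, and on that schedule the table leaves at most the Week 96 row. This stands as a limit on size. It does not settle the matter, because Protocol 4.5.10 has all patients scanned at Weeks 24, 48 and 72, and Protocol 3.1.1.4 runs FU1 visits in parallel with the double-blind schedule.

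Every affected scan also sits nominally on the cut date. With a ±4-week window, some will fall after it and be removed anyway. That stands too.

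Early switching may be uncommon. Patients remain blinded after withdrawal, and Protocol 4.4.3 discourages several MS drugs while B cells are depleted. Protocol 4.3.2.1 states a 22-week minimum between ocrelizumab doses; if commercial ocrelizumab respected it, a kept scan on the cut date would be at most 24 − 22 = 2 weeks into the new drug. But Protocol 4.2 allows unblinding to guide later care, and no interval is stated for other drugs.

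The safety comparison is loose, since exposure duration serves another purpose. It shows only that the switch date is available and is used as a stop elsewhere.

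A reader might infer that placebo patients moving to an effective drug pull the MRI results towards no difference. The documents do not support that as a finding. They give no switching rate, timing or effect of the new drugs, and patients on ocrelizumab can switch as well. Nor should a reader infer that several scans per switcher are kept, or that the primary endpoint is affected: SAP 4.2.2 already handles the switch.

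**Conclusion.** The inconsistency is real on the text. The MRI estimands exclude initiation of another MS drug, the data rule does not act on it, and no other part of the SAP supplies an earlier cut for MRI. SAP 4.8 explains the change to lesion radius but says nothing on this.

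It is a minor point. The bound is one scheduled scan per patient who switches within 24 weeks of the last dose, and zero for many patients if FU1 scans are 48-weekly. The bound assumes visits on the nominal calendar; delayed doses or visits could shift individual cases. The size and direction of bias cannot be computed from the documents. The mismatch between estimand and data rule does not depend on either.

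**What to change.** In SAP 4.3.2 and 4.3.3, under the switch event, state that MRI data are set to missing after the earlier of (a) last dose + 24 weeks and (b) the start of another MS DMT or commercial ocrelizumab. Leave the rule for stopping without a switch as it is. Sections 4.4.5 and 4.4.6 then follow by their cross-references.

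No new data are needed, because 4.2.2 and 4.5.1.2 already require the switch date. The cost is one clause, made before unblinding, and a few lost scans. In the example above, the patient would have no brain-volume slope observation left and one T2 observation instead of two.
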